## 5. STATISTICAL CONSIDERATIONS

### Study Objective and Primary Endpoint

The primary objective of this study is to compare progression-free survival of RARC versus ORC in patients with bladder cancer. More specifically, the primary endpoint for this study is progression-free survival at 2 years. This is a non-inferiority comparison, i.e. the study will test whether the robotic-assisted cystectomy is, at worst, inferior to the open radical cystectomy by a small pre-defined margin. This study will use a centralized dynamic allocation procedure to allocate an equal number of patients to each of the treatment arms. The procedure will balance the marginal distribution of the stratification factors between these two treatments.

### Power and Significance

The margin for this study is 15% which means that RARC would be considered inferior if the true progression free survival at two years was more than 15% lower than the progression-free survival at two years in the ORC arm. A total of 288 evaluable patients (144 patients per arm) yield a study with 80% power and a two-sided significance level, alpha, of 5% to correctly reject the null-hypothesis of unacceptable inferiority. These calculations are based on the assumption that progression-free survival at two years in the patients receiving ORC is approximately 71% and that the rate of progressions at two years is binomially distributed. Evaluable patients are defined as eligible patients who have no major protocol deviations and have 90-day post-surgery follow-up data. Major protocol deviations will be recorded for patients with no surgery given, where surgery was started correctly but discontinued before cystectomy was completed; or where the patient received a surgery type different from their randomization assignment for any reason. In addition, a major protocol deviation will be recorded if the surgery begins as assigned, but the robotic procedure is aborted and an open procedure is required to complete the operation.

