### Submission and processing of specimens

The cystectomy specimen (with or without uterus, ovaries, or vaginal cuff in females and prostate in males) will be submitted en bloc, processed and assessed in a standardized fashion at all the participating institutions for margin status along with histology, size, stage, grade and presence/absence of lymphovascular invasion. At a minimum the LND will be submitted in two separate packets labeled left and right pelvic. All of these regions may be submitted in smaller packets (e.g. external iliac, obturator, internal iliac) at the surgeons preference. The standardized Cystectomy Pathology Form will be submitted to CRAB.

The perioperative care measures will be performed per institutional standard based on each institution's policy.

**Progression free survival:** From the date of surgery to the date of first documentation of progression or death due to any cause. Patients last known to be alive and progression-free are censored at the date of last contact. Progression will be determined using RECIST 1.1 criteria by the treating physician based on radiographic or pathologic evidence of disease progression, or death from disease. Any documented recurrence will be considered progression. All patients will have been followed for at least 2 years and 65% of patients will have been followed for 3 years.

**Overall survival:** From date of surgery to date of death due to any cause. Patients last known to be alive are censored at the date of last contact.

Serum hemoglobin and a comprehensive metabolic panel (CMP) will be measured on 10 cc of blood obtained by a venipuncture. These laboratory parameters are part of a routine preoperative work up and postoperative follow up in patients undergoing radical cystectomy and urinary diversion. No extra laboratory tests will be administered to the subjects enrolled in this trial.

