### **Analysis of Primary Endpoint**

A one-sided mantel-Haenszel test with half the alpha (0.025) will be used for testing the primary non-inferiority hypothesis that compares progression free survival at two years in the two treatment arms.

In superiority trials the intent to treat (ITT) population is widely accepted as the analysis population for the primary endpoint as it gives the most conservative result of such a study. In contrast, for non-inferiority trials the inclusion of ineligible or untreated patients or the lack of adherence to the assigned treatment is expected to increase the noise of the study and make the two treatment arms look more alike, thus the overall results of the study less conservative. Thus we will use the per-protocol (PP) population as the analysis population for the primary endpoint. We will also perform a sensitivity analysis of the primary endpoint using the ITT population. These two analysis populations are defined below. The design and analysis of this trial are based on the SWOG standards for noninferiority trials, which are detailed the chapter 12 in the Handbook for Statistics in Clinical Oncology, second edition, Chapman & Hall 2006.

Serum hemoglobin, serum creatinine and serum albumin levels will be taken at baseline and at a variety of time points post-surgery throughout the study. Linear mixed effects will be used to compare these blood levels and their changes over time between the two treatment groups.

QOL outcomes will be measured at baseline and in the post-operative period at 3 and 6 months using the Functional Assessment of Cancer Therapy – Vanderbilt Cystectomy Index (FACT-VCI) as well as the Short Form 8 (SF-8) Questionnaires. Simple descriptive statistics, such as mean and standard deviation, will be used to summarize the FACT-VCI and the SF-8 scores at each time point and for each treatment group. A multivariate linear mixed effects model will then be fitted to each score in this repeated measures design. The main effect will be visit (at baseline, 3 and 6 months) and will be treated as a categorical variable to accommodate for the non-linear trends. If the exact time corresponding to a particular visit differs significantly between patients a variable

representing the deviation from the visit-specific mean time will be added to the model. Standard diagnostic tools will be used to assess model fit.

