### **Analysis Populations:**

#### **Per Protocol Population (PP Population):**

The per-protocol population includes all patients who have met inclusion/exclusion criteria and received the surgery to which they were randomized. This is the primary efficacy population. All efficacy and QL endpoints will be assessed using this population.

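### Evaluability is set by 90-day data although the power calculation needs a two-year outcome, and the powered set differs from the per-protocol set that will be analysed

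*Combined protocol and SAP*

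**What the plan says.** All references are to the combined protocol and SAP.

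- **Endpoint.** Study Objective and Primary Endpoint: "the primary endpoint for this study is progression-free survival at 2 years".
- **Sample size.** Power and Significance asks for 288 evaluable patients, 144 per arm, for 80% power. It uses a 15-point margin, 71% two-year progression-free survival (PFS) on ORC, and the assumption that "the rate of progressions at two years is binomially distributed".
- **Who counts towards the 288.** Same section: "Evaluable patients are defined as eligible patients who have no major protocol deviations and have 90-day post-surgery follow-up data". Major deviations there include no surgery, an uncompleted cystectomy, the wrong operation, and robotic-to-open conversion.
- **Who is analysed.** Analysis of Primary Endpoint names the per-protocol population, with intent-to-treat as sensitivity analysis. Under Analysis Populations, the per-protocol set "includes all patients who have met inclusion/exclusion criteria and received the surgery to which they were randomized". Neither 90-day data nor conversion is mentioned.
- **Test.** "A one-sided mantel-Haenszel test with half the alpha (0.025) will be used for testing the primary non-inferiority hypothesis".
- **Events and censoring.** The PFS definition in Section 4 runs from surgery and counts death from any cause. It adds: "Patients last known to be alive and progression-free are censored at the date of last contact".
- **Accrual.** Accrual and Study Duration plans about 350 patients, a maximum drop-out of 10%, and at least two years of follow-up for all.

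**The concern.** A two-year binomial calculation uses one yes/no result per patient at two years. Ninety days of data do not supply it. A patient who is event-free when lost at month 4 is evaluable by definition and censored under the PFS definition. No section says how such a patient enters the two-year Mantel-Haenszel comparison. Reaching 288 evaluable patients therefore does not by itself secure the stated power.

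The document also describes the primary set in two ways: the set that was powered has a 90-day condition, and the set that will be analysed has none. The difference touches early postoperative deaths. If the sample-size definition were carried into the analysis, a death on day 40 could be read as lacking 90-day data and be removed, although the endpoint counts it as an event. In a non-inferiority comparison of two operations, that should not be left to interpretation.

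**Working it through.** **Inputs from the documents:** ORC two-year PFS 0.71; margin 0.15; one-sided alpha 0.025; power 0.80; 1:1 allocation; 350 accrued; 10% drop-out. **Assumed:** RARC two-year PFS also 0.71 for power (no separate rate is given), and the rates of later loss and early death used below (the documents give none).

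**1. Reproduce the plan's figure.**
n per arm = (1.960 + 0.842)² × 2 × 0.71 × 0.29 / 0.15² = 143.7, rounded up to 144, or 288 in total.
Power at 144 per arm = Φ(0.15 / √(2 × 0.71 × 0.29 / 144) − 1.960) = Φ(2.805 − 1.960) = 80.1%.
The figure reproduces, with all 288 contributing a two-year outcome.

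**2. Power if only 288 are evaluable at day 90 and some then lack two-year status.**

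| Later loss (assumed) | With two-year status | Power |
|---|---|---|
| 5% | 273.6 | 78.1% |
| 10% | 259.2 | 75.8% |
| 15% | 244.8 | 73.4% |
| 20% | 230.4 | 70.8% |

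**3. Add the planned accrual.**
288 / 0.9 = 320, so 350 is 30 more than a 10% drop-out requires.
350 × 0.9 = 315, giving power 83.5%.
Loss tolerated while keeping 288: 1 − 288/350 = 17.7% in total; or, if the 10% is used up before day 90, 1 − 288/315 = 8.6% afterwards.
From 315, a further 5%, 10% or 15% loss leaves 299.25, 283.5 or 267.75 patients, with power 81.6%, 79.5% or 77.2%.

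**4. Early deaths, only if the evaluable definition became the analysis set and early deaths were read as non-evaluable.**
Take the truth at the margin: ORC 0.71, RARC 0.56. Removing a share d of early deaths turns PFS S into S/(1 − d) and n into 144(1 − d). The probability of wrongly claiming non-inferiority is Φ((0.15 − difference)/SE − 1.960), with unpooled SE.

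| Early mortality, ORC v RARC (assumed) | Apparent PFS | Difference | One-sided error |
|---|---|---|---|
| 5% v 2% | 0.7474 v 0.5714 | 0.176 | 0.008 |
| 2% v 2% | 0.7245 v 0.5714 | 0.153 | 0.022 |
| 5% v 5% | 0.7474 v 0.5895 | 0.158 | 0.018 |
| 2% v 5% | 0.7245 v 0.5895 | 0.135 | 0.045 |

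The nominal value is 0.025. Error rises above it here only where early mortality is higher on RARC.

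**The case against.** The strongest reply is that the evaluable definition appears once, in the sample-size paragraph, and is never named as an analysis set. The analysis sections name the per-protocol population. A patient who dies on day 40 after the assigned operation belongs to it, the death is an event, and the Death Report Form captures it. Intent-to-treat gives a further check. Moreover, a patient known to have died has a known status at day 90, so even the evaluable wording need not exclude that patient. This reply stands. A reader might infer that the plan drops early deaths and so inflates the type I error; the documents do not support that. The 0.045 needs two readings the text does not settle, plus higher early mortality on RARC, for which the documents give no figure.

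On power, the reply is that 350 are accrued and all are to be followed for two years. This stands in large part. A reader might infer from the 288-based table that the trial is underpowered; the documents do not show that. The loss model is also severe, since a patient who progresses before being lost has a known outcome. Two limits remain. The 17.7% allowance must absorb ineligibility, absent or uncompleted surgery, crossover, conversion and loss to two years, and the plan does not say which of these the 10% covers. Two-year follow-up is also an intention: the Subject Completion and Withdrawal section allows a patient to leave at any time.

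Neither reply removes the mismatch between the two definitions or supplies a rule for patients censored before two years.

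**Conclusion.** The point holds as a mismatch of definitions with a missing analysis rule. The 90-day condition does not fit a two-year endpoint, the powered and analysed sets differ, and patients censored before two years have no stated place in the primary comparison.

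The size is modest. Power is 80.1% if exactly 288 patients give two-year information and 83.5% at 315. It stays at or above 80% until total loss exceeds 17.7% of 350, or 8.6% after day 90 from 315. These figures assume equal true PFS of 71% in both arms and no information from a lost patient. The early-death effect is conditional on the evaluable definition governing the analysis. Across the assumed mortality rates, the one-sided error at the margin ranges from about 0.008 to 0.045.

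This should be settled before analysis, but it ranks below a must-fix: the sample size itself is correct for its stated inputs, and the named primary population counts early deaths.

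**What to change.** 1. In Power and Significance, delete the 90-day data condition and make the powered set identical to the per-protocol population. In reconciling the two, state in the population definition whether the listed major deviations, including uncompleted cystectomy and conversion, lead to exclusion.
2. State that any death within two years of surgery, including before day 90, is a primary-endpoint event.
3. Keep patients censored before two years in the primary comparison through a censoring-aware estimate. One option is the difference in Kaplan-Meier PFS at two years, with its confidence limit set against the 15-point margin. The plan already uses Kaplan-Meier for PFS and overall survival.
4. Say what the 10% drop-out covers, and restate power for the number expected to give two-year information.

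Do not restrict the set to patients with known two-year status. That would keep patients who had an event before being lost while removing event-free patients lost early, which biases two-year PFS downward. In the per-protocol definition it would also remove patients from quality-of-life and other efficacy analyses, such as hand grip, blood loss and length of stay, whose data were already observed.

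The cost is wording plus a changed primary estimator. No new data are needed. The restated power may be a little lower or higher than 80%, depending on the loss expected.

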### Stratification Factors

Because outcomes may vary by type of urinary diversion (ideal conduit or neobladder), we will also stratify by the clinical T stage of condition (T1, T2, T3, T4) and neo adjuvant chemotherapy since it directly influences oncologic outcomes.

### **Accrual and Study Duration**

We anticipate participation of 15 sites and an accrual of approximately 110 eligible patients per year. Assuming a maximum drop-out rate of 10%, a total of approximately 350 patients (approximately 175 patients in each arm) will be accrued to this study. Thus approximately 350 patients will be accrued in approximately three years. All patients will be followed for at least two years for progression. Based on the accrual estimates, after three years of accrual and two additional years of follow-up, 65% of patients will have follow up available to evaluate progression free survival at 3 years. Thus the study duration is expected to be approximately five years.

### **Analysis of Primary Endpoint**

A one-sided mantel-Haenszel test with half the alpha (0.025) will be used for testing the primary non-inferiority hypothesis that compares progression free survival at two years in the two treatment arms.

In superiority trials the intent to treat (ITT) population is widely accepted as the analysis population for the primary endpoint as it gives the most conservative result of such a study. In contrast, for non-inferiority trials the inclusion of ineligible or untreated patients or the lack of adherence to the assigned treatment is expected to increase the noise of the study and make the two treatment arms look more alike, thus the overall results of the study less conservative. Thus we will use the per-protocol (PP) population as the analysis population for the primary endpoint. We will also perform a sensitivity analysis of the primary endpoint using the ITT population. These two analysis populations are defined below. The design and analysis of this trial are based on the SWOG standards for noninferiority trials, which are detailed the chapter 12 in the Handbook for Statistics in Clinical Oncology, second edition, Chapman & Hall 2006.

Serum hemoglobin, serum creatinine and serum albumin levels will be taken at baseline and at a variety of time points post-surgery throughout the study. Linear mixed effects will be used to compare these blood levels and their changes over time between the two treatment groups.

QOL outcomes will be measured at baseline and in the post-operative period at 3 and 6 months using the Functional Assessment of Cancer Therapy – Vanderbilt Cystectomy Index (FACT-VCI) as well as the Short Form 8 (SF-8) Questionnaires. Simple descriptive statistics, such as mean and standard deviation, will be used to summarize the FACT-VCI and the SF-8 scores at each time point and for each treatment group. A multivariate linear mixed effects model will then be fitted to each score in this repeated measures design. The main effect will be visit (at baseline, 3 and 6 months) and will be treated as a categorical variable to accommodate for the non-linear trends. If the exact time corresponding to a particular visit differs significantly between patients a variable

representing the deviation from the visit-specific mean time will be added to the model. Standard diagnostic tools will be used to assess model fit.

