##### Specific Aim 2 :

1. Serum Hemoglobin, Serum Creatinine and Serum Albumin levels at baseline and in the post operative period at 4-6 weeks, 3 months, 6 months, 12 months, 24 months, and 36 months.
2. Quality of Life (QOL) outcomes at baseline and in the post operative period at 3 months and 6 months using the Functional Assessment of Cancer Therapy - Vanderbilt Cystectomy Index (FACT-VCI) as well as the Short Form 8 (SF-8) Questionnaires.

3. Compare surrogates of surgical quality by evaluating surgical margin status and number of lymph nodes harvested.
4. Compare surgical morbidity by evaluating complication rates at 90 days post operative using the modified Clavien grading system.
5. Perioperative measures such as Estimated Blood Loss (EBL), Blood transfusion rates, total intraoperative fluid requirements, total operative time, total postoperative length of hospital stay and analgesic requirement.
6. *3 year progression free survival in 65% of patients.*

Specific Aim 3 :

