Hand Grip Strength at 3 months after surgery will be measured as a surrogate for recovery after surgery. It was found that only 39% of patients recovered at three months after a major abdominal surgery as measured by the Hand Grip Strength. We will compare the proportion of patients recovered as measured by Hand Grip Strength between the two treatment arms. We hypothesize that 20% more patients will have recovered three months after surgery in the RARC arm compared to the ORC arm. A total of 288 patients yield 91% power and a one-sided significance level of 0.025 to detect a difference between arms of at least 20%. These calculations are based on the assumption that Hand Grip Strength at three months is binomially distributed. Surgical margin as a measure for local cancer control will be measured as positive or negative for each patient and compared between arms using a Fisher's exact test. The number of nodes resected in each arm will be compared using a t-test.

Progression-free and overall survival will be evaluated using the method of Kaplan Meyer and comparisons between arms will be made using the stratified log-rank test.

All efficacy and QL endpoints will be assessed using the PP population.

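### The quality-of-life mixed model names visit as its main effect but no treatment term or contrast, so as written it gives no RARC v ORC test, and the handling of baseline is left open

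*Combined protocol and SAP*

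**What the plan says.** Section 3, Specific Aim 2, which stands under the Primary End Points heading, lists "Quality of Life (QOL) outcomes at baseline and in the post operative period at 3 months and 6 months", using FACT-VCI and SF-8. Section 5, Analysis of Primary Endpoint, repeats the schedule ("QOL outcomes will be measured at baseline and in the post-operative period at 3 and 6 months") and then sets out the analysis in three steps:

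- **Descriptive.** Means and standard deviations "will be used to summarize the FACT-VCI and the SF-8 scores at each time point and for each treatment group". This is the only place where arm appears in the QOL analysis.
- **Model.** "A multivariate linear mixed effects model will then be fitted to each score in this repeated measures design".
- **Terms.** "The main effect will be visit (at baseline, 3 and 6 months) and will be treated as a categorical variable". If visit times differ markedly between patients, a variable "representing the deviation from the visit-specific mean time will be added to the model".

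The paragraph just before, on haemoglobin, creatinine and albumin, does state a comparison of arms: "Linear mixed effects will be used to compare these blood levels and their changes over time between the two treatment groups". On the analysis set, the Secondary Endpoints text says "All efficacy and QL endpoints will be assessed using the PP population". No hypothesis test, effect size, standard deviation, power or significance level is stated for QOL.

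**The concern.** A visit effect answers whether scores move between baseline, 3 months and 6 months. It does not answer whether they move differently after robotic and open surgery. The Background section gives the untested possibility of better QOL with the robotic technique as part of the case for the trial. Since no power or hypothesis is stated for QOL, this model paragraph is the whole inferential plan for it.

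If the treatment terms are not written down, the analyst must choose them later, when by-arm summaries may already have been seen. Several models fit the text. They differ in what they estimate (a difference at 3 months, at 6 months, an average, or a change from baseline) and in precision.

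**Working it through.** **1. The plan's own figure.** From Power and Significance: ORC 2-year PFS 71%, margin 15 points, 80% power, one-sided 0.025. Per arm, n = (1.960 + 0.842)² × 2 × 0.71 × 0.29 / 0.15² = 7.849 × 0.4118 / 0.0225 = 143.7, so 144 per arm and 288 in total. This reproduces. The figure belongs to PFS; it is used below only to put a scale on the QOL contrasts.

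**2. What the stated model estimates.** Suppose the true mean change from baseline to 6 months is a + d/2 in RARC and a − d/2 in ORC. With equal arms and visit as the only fixed effect, the 6-month visit effect is [(a + d/2) + (a − d/2)] / 2 = a, whatever d is. The model has no parameter for d. The timing covariate does not supply one.

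**3. How much the handling of baseline matters.** The documents give no correlation or standard deviation. Assumptions: 144 per arm with complete data, equal correlation rho between visits, results in standard deviation (SD) units. Standard error (SE) of the arm difference at one follow-up visit:

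- post-only (arm means free at baseline, follow-up difference read off): √(2/144) = 0.118
- change from baseline: √(2/144) × √[2(1 − rho)]
- baseline as covariate: √(2/144) × √(1 − rho²)

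| rho (assumed) | SE post-only | SE change | SE adjusted | Variance saved v post-only (rho²) | Variance saved v change ((1 − rho)/2) |
|---|---|---|---|---|---|
| 0.3 | 0.118 | 0.139 | 0.112 | 9% | 35% |
| 0.5 | 0.118 | 0.118 | 0.102 | 25% | 25% |
| 0.7 | 0.118 | 0.091 | 0.084 | 49% | 15% |

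Differences detectable with 80% power at two-sided 5% are 0.330 SD for post-only at every rho. At rho 0.3 / 0.5 / 0.7 they are 0.391 / 0.330 / 0.256 SD for change and 0.315 / 0.286 / 0.236 SD with adjustment.

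**4. Baseline kept as a visit, with one mean common to both arms.** Generalised least squares under the same assumptions gives SEs of 0.112 / 0.102 / 0.084, identical to the baseline-as-covariate column. Against that model, covariate adjustment saves nothing.

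**5. One conditional case.** If arm were added only as a main effect across all three visits, with a true effect of 0 at baseline and d at 3 and 6 months, the estimate under equal correlation and complete data would be (0 + d + d)/3 = 2d/3.

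**The case against.** The best defence is that this is an omission of wording, not a decision against comparing the arms. Summaries are planned by arm, the laboratory sentence next to it compares arms, and the Background states a QOL hypothesis. The visit sentence may only explain how time is coded, to allow for non-linear trends, and need not be a full list of terms. It stands that a comparison is very probably intended. It does not close the gap, because intent does not say which contrast, at which visit, with what treatment of baseline.

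Four stronger readings are tempting, and the documents do not support them.

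- *The baseline score is wasted.* Entering baseline as a level of visit is a recognised use of it, and with a common baseline mean it is as precise as covariate adjustment (step 4). Precision is lost only if baseline means are left free by arm, on which the text is silent.
- *The QOL effect will be diluted to 2d/3.* That applies only to a model with visit plus a plain arm effect, which the plan does not state. The laboratory wording, which compares changes over time between groups, points if anything towards arm-by-time.
- *Randomisation guarantees equal baseline means, so a constrained model is automatically safe.* QOL is analysed per protocol, in patients selected after randomisation for having received their assigned surgery. Power and Significance counts conversion from robotic to open as a major deviation, which can arise in one arm only. If that rule carries over to the per-protocol set, selection can differ by arm. In that set equal baseline means are an assumption.
- *The laboratory models share the defect.* Their paragraph already states a comparison between arms of levels and of changes.

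**Conclusion.** The point holds as a gap in specification. The QOL model as written contains no treatment parameter, and nothing elsewhere in the documents supplies one, so the planned inferential analysis would not yield a between-arm result for an outcome listed in Specific Aim 2. That conclusion needs no assumed numbers.

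The size of the baseline issue is conditional. Over rho from 0.3 to 0.7, adjustment reduces the variance by 9% to 49% against a post-only contrast and by 35% down to 15% against a change contrast. The saving is nil if a common baseline mean was meant. These figures rest on assumed correlations, equal correlation between visits and complete data. The matter should be settled before QOL data are compared by arm, but it does not touch the primary PFS comparison.

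**What to change.** Replace the model sentence with a full specification. For each QOL score, fit a linear mixed model to the 3- and 6-month scores, with baseline score as a covariate and with visit, arm, arm-by-visit and the stratification factors (diversion type, clinical T stage, neoadjuvant chemotherapy) as fixed effects. The tests are the RARC v ORC contrasts at 3 months and at 6 months. State the significance level and how the two contrasts are to be read together.

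A constrained model with baseline as a response and one baseline mean for both arms is an alternative in the intent-to-treat population. It also retains patients who have only a baseline score. If it is used in the per-protocol population, the plan should say that equal baseline means are assumed there.

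The cost is a change of SAP wording. All the scores and factors are already collected, and no patients, visits or forms are added.
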